4 STUDY ENDPOINTS

4.1 **Primary Endpoints**

- Product Safety as defined by the incidence, type and severity of treatment-related adverse events (AEs) and serious adverse events (SAEs) at Month 1, 2, 3, 6, 12
- Change from baseline in Cerebrospinal Fluid (CSF) heparan sulfate levels after treatment at Month 1, 6, 12
- Change from baseline in liver and/or spleen volumes after treatment, as measured by magnetic resonance imaging (MRI) at Month 1, 6, 12

4.2 Secondary Endpoints

- Change from baseline in plasma or urine glycosaminoglycans or heparan sulfate after treatment at Month 1, 6, 12
- Change from baseline in CSF or plasma or leukocyte SGSH enzyme activity levels after treatment at Month 1, 6, 12
- Change from baseline in brain volumes after treatment, as measured by MRI at Month 12
- Change from baseline in sleep pattern as measured by the modified Children's Sleep Habits Questionnaire (CSHQ) at Month 6, 12
- Change from baseline in Pediatric Quality of Life Inventory (PedsQL[™]) Core Generic Scales total score at Month 6, 12
- Change from baseline in parent quality of life, using the Parenting Stress Index, 4th Edition (PSI-4) at Month 6, 12
- Change from baseline in gastrointestinal symptoms using the PedsQLTM Gastrointestinal Symptoms Scales at Month 6, 12
- Parent Global Impression Score at Month 6, 12
- Clinical Global Impression Improvement Scale at Month 6, 12
- Change from baseline in Parent Symptoms Score Questionnaire at Month 6, 12
- Change from baseline in Body Mass Index (BMI) after treatment at Month 6, 12
- Incidence and change from baseline in abnormalities in standard awake 45-minutes-EEG monitoring at Month 6, 12
- Determination of vector shedding analysis in plasma, saliva, urine and feces will provide preliminary data for the Environmental Risk Assessment (ERA)

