4.2. Inclusion/Exclusion Criteria

4.2.1. Inclusion Criteria

1. Diagnosis of MPS IIIA confirmed by the following methods:
 - a. No detectable or significantly reduced SGSH enzyme activity by leukocyte assay, and
 - b. Genomic DNA analysis demonstrating homozygous or compound heterozygous mutations in the SGSH gene
2. Cognitive Development Quotient (DQ) lower than 60 (calculated by Bayley Scales of Infant and Toddler Development - Third Edition)
3. Must be ambulatory, though may receive assistance with ambulation
4. Age range of 2 years up to 18 years (excluded).

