5.1 Intent-to-Treat Set (ITT)

The ITT Set will include all enrolled subjects who received ABO-102 and have at least one post-baseline efficacy measurement. Efficacy and safety analyses will be conducted based on the ITT Population.

The primary endpoints, secondary endpoints, **CCI** endpoints will be analyzed using the ITT Set. At the time of the study termination, all 5 enrolled subjects were treated and had at least one post-baseline assessment. Therefore, the ITT Population is equivalent to all patients enrolled and will be used to evaluate both safety and efficacy data and for populating listings.

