8.2.2 Analyses of Secondary Efficacy Endpoints

- Change from baseline in plasma or urine glycosaminoglycans or heparan sulfate after treatment at Month 1, 6, 12
- Change from baseline in CSF or plasma or leukocyte SGSH enzyme activity levels after treatment at Month 1, 6, 12
- Change from baseline in brain volumes after treatment, as measured by MRI at Month 12
- Change from baseline in sleep pattern as measured by the modified CSHQ at Month 6, 12
- Change from baseline in PedsQLTM Core Generic Scales total score at Month 6, 12
- Change from baseline in parent quality of life, using the PSI-4 at Month 6, 12

[figure not shown]
- Change from baseline in gastrointestinal symptoms using the PedsQL[™] Gastrointestinal Symptoms Scales at Month 6, 12
- Change from baseline in Parent Symptoms Score Questionnaire at Month 6, 12
- Parent Symptoms Score Questionnaire at Month 6, 12
- Parent Global Impression Score at Month 6, 12
- Clinical Global Impression Improvement Scale at Month 6, 12
- Incidence and change from baseline in abnormalities in standard awake 45-minutes-EEG monitoring at Month 6, 12

All of the above secondary efficacy endpoints will be presented by listings only.

• Determination of vector shedding analysis in plasma, saliva, urine and feces will provide preliminary data for the ERA

Vector shedding samples will continue to be collected and analyzed until two consecutive negative samples are collected or completion of the study by the subject, whichever comes first.

Observed values and change from baseline in copies per 1mL of specimen in plasma, saliva, urine and feces will be summarized descriptively at baseline and each post-baseline time point. Copies per 1mL of specimen in feces will be presented as a spaghetti plot over each visit by subject.

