8.3.3 Vital Signs and Physical Examination

Vital Signs

Vital signs will include weight, height, BMI, head circumference, body temperature, heart rate, respiratory rate, pulse oximetry, and systolic and diastolic blood pressure for all time

points. Summary statistics will be calculated at baseline and follow-up time points as well as the nominal and percent changes from baseline for each visit.

Physical Exams

Adverse physical examination changes are captured as AEs. Physical Exam findings and vital signs will be included in the listings. Physical exam findings will be listed at each visit.

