8.4.2 Body Mass Index (BMI)

BMI is the subject's body weight in kilograms divided by the square of the subject's height in meters.

 $BMI = weight in kilograms / (height in meters)^2$

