10 CHANGES FROM THE PROTOCOL

Due to the study early termination and only 5 subjects being enrolled, there will be no comparison to natural history study data.

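### BMI change is a secondary endpoint in growing children but is summarised only as raw and percent change; an age- and sex-standardised score should sit beside it

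*SAP*

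**What the plan says.** - SAP 4.2 lists among the secondary endpoints "Change from baseline in Body Mass Index (BMI) after treatment at Month 6, 12". Protocol 5.7 has the same outcome with Months 18 and 24 as well.
- SAP 8.4.2 gives the only derivation: "BMI = weight in kilograms / (height in meters)^2".
- SAP 8.3.3, a safety section, places BMI with the vital signs: "Vital signs will include weight, height, BMI, head circumference, body temperature, heart rate" and others. It plans summary statistics at baseline and follow-up, plus "the nominal and percent changes from baseline for each visit".
- SAP 8.2.2 does not name BMI. The endpoints it does name, apart from vector shedding, fall under this sentence: "All of the above secondary efficacy endpoints will be presented by listings only".
- Protocol 4.2.1 admits children from 2 years to under 18 years. SAP 5.1 records that "all 5 enrolled subjects were treated and had at least one post-baseline assessment".
- The trial has one arm, and SAP 10 states: "Due to the study early termination and only 5 subjects being enrolled, there will be no comparison to natural history study data".

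Neither document mentions a BMI z-score, a percentile, a growth reference, or any age or sex adjustment of BMI.

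**The concern.** In childhood the expected BMI depends on age and sex, and it moves over 6 to 12 months without any intervention. It can fall at some ages and rise at others. A raw change therefore has at least two parts: the change expected of any child of that age and sex, and the departure from it. Only the second part could bear on the product, and the planned summary does not show it. Percent change does not help, because it divides by the child's own baseline and not by what is expected at the later age.

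The SAP already allows for age elsewhere: the developmental quotients in 8.4.3 to 8.4.5 divide by chronological age. BMI gets no comparable step. At stake is how the table is read. A fall or rise in mean BMI could be taken as a change after treatment when it is ordinary growth, or ordinary growth could mask a real departure.

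**Working it through.** The plan states no expected effect, SD, power or alpha for BMI, so there is no figure of its own to reproduce. The documents give no individual ages, sexes, heights or weights. All growth figures below are assumptions chosen for illustration.

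**1. Raw BMI change from growth alone.** If height rises by a fraction gh and weight by gw, the fractional change in BMI is (1 + gw)/(1 + gh)² − 1. For 12-month weight gains of 5% to 20%:

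| Height gain | BMI change at 5% weight gain | BMI change at 20% weight gain | Weight gain that holds BMI level, (1 + gh)² − 1 |
|---|---|---|---|
| 3% | 1.05/1.0609 − 1 = −1.0% | 1.20/1.0609 − 1 = +13.1% | 6.1% |
| 5% | 1.05/1.1025 − 1 = −4.8% | 1.20/1.1025 − 1 = +8.8% | 10.3% |
| 8% | 1.05/1.1664 − 1 = −10.0% | 1.20/1.1664 − 1 = +2.9% | 16.6% |

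At an assumed baseline of 16 kg/m², the whole grid runs from −1.6 to +2.1 kg/m². This grid deliberately crosses all the gains. It shows that either sign is possible, not what is likely in these children.

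**2. Two assumed children over 12 months.**

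- From 100 cm and 16.0 kg to 107 cm and 17.8 kg: 16.0/1.00² = 16.00 and 17.8/1.07² = 15.55, a change of −0.45 kg/m² (−2.8%).
- From 130 cm and 30 kg to 136 cm and 34 kg: 30/1.30² = 17.75 and 34/1.36² = 18.38, a change of +0.63 kg/m² (+3.6%).

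The gap between them is 0.63 + 0.45 = 1.08 kg/m². It follows from the two children chosen.

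**3. Effect on a mean of five.** Suppose k children drift by −d and 5 − k by +d. The mean is d(5 − 2k)/5. With an assumed d of 0.5 kg/m², it takes the values +0.5, +0.3, +0.1, −0.1, −0.3 and −0.5 as k goes from 0 to 5. If all five are of similar age there is no cancelling, but the common drift stays in the mean in full.

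**4. Precision, for context.** With n = 5, the 95% half-width of a mean change is t(0.975, 4)/√5 = 2.776/2.236 = 1.24 SD. The SAP plans no interval or test for BMI, so drift is one of two reasons to read the mean cautiously.

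**5. Can the standardised score be derived?** Yes. Protocol 5.3.1 collects date of birth, gender, height and weight at Screening Visit 1, and 5.5.2.10 and 5.5.2.11 collect height and weight at Day 180 and Month 12.

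**The case against.** The strongest reply is that little hangs on this. BMI is one of 13 secondary endpoints in SAP 4.2, summarised descriptively in five children, with no test, success criterion or decision rule. The SAP reports it under safety and nowhere says it will be read as a treatment effect. SAP 8.1, 8.1.1 and 8.3.3 also plan by-subject listings that include vital signs, so each child's values will be visible and a z-score could be derived later. All of that stands, and it keeps the point minor. It does not remove it: a growth reference chosen after the data are seen is a weaker basis than one named beforehand, and the summary table is what most readers will use.

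Four stronger readings are tempting and are not supported:

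- **That the endpoint has no analysis, because 8.2.2 omits it.** It has one in 8.3.3, and a fuller one than the listings-only endpoints receive.
- **That the five children are of mixed age, so opposite drifts will cancel.** The 2-to-under-18 range is an eligibility limit. The enrolled ages are not given.
- **That dropping the natural-history comparison removed a control for BMI.** In Protocol 5.7 only the Mullen, Bayley and Vineland outcomes carry that comparison. Only a general sentence in the synopsis could extend it to BMI.
- **That a z-score would isolate the product's effect.** It removes only the growth expected in the reference population. Disease course (Protocol 3.1 describes skeletal changes and, later, swallowing problems) and the prednisone or prednisolone course would still be mixed in.

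**Conclusion.** The point holds as a minor one. The planned BMI summary uses a scale that includes expected age- and sex-related change, and nothing else in the plan takes that change out. Under the assumed growth paths this amounts to roughly half a kg/m² in either direction over 12 months. The true size and sign for these five children cannot be stated from the documents.

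The conclusion rests on two things: the text, where BMI appears only in kg/m² with nominal and percent change, and the general fact that expected BMI varies with age and sex in childhood. It is a risk of misreading a descriptive table, not an error in any stated figure. It does not show that the reported change will be misleading in this sample.

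**What to change.** 1. In SAP 8.4.2, add a BMI-for-age-and-sex z-score from one named growth reference. State that age is exact age at the measurement date: the 30-day month in 8.4.1 would count a 365-day interval as 365/30 = 12.2 months.
2. In SAP 8.3.3, report that z-score at baseline, Month 6 and Month 12, with its change from baseline, by child (showing age and sex) and in summary. Keep raw BMI alongside.
3. Cross-refer the BMI endpoint in 4.2 to 8.3.3. Do not add it to the list in 8.2.2, where the listings-only sentence would conflict with the summary already planned.
4. Add one sentence saying that the z-score accounts for reference-population growth only and does not separate a product effect from disease course or the steroid course.

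The cost is a few lines of SAP text and one standard derivation. No new data, visits or procedures are needed. The downside is that a reference must be chosen and justified.

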4.3 Exploratory Endpoints

- CCI
- •
- •
- •

• CCI

5 ANALYSIS SETS

The following population will be defined for study summaries and analyses.

5.1 Intent-to-Treat Set (ITT)

The ITT Set will include all enrolled subjects who received ABO-102 and have at least one post-baseline efficacy measurement. Efficacy and safety analyses will be conducted based on the ITT Population.

The primary endpoints, secondary endpoints, **CCI** endpoints will be analyzed using the ITT Set. At the time of the study termination, all 5 enrolled subjects were treated and had at least one post-baseline assessment. Therefore, the ITT Population is equivalent to all patients enrolled and will be used to evaluate both safety and efficacy data and for populating listings.

6 INTERIM ANALYSIS

Interim analysis will not be conducted due to the early study termination.

7 STUDY SUBJECTS

7.1 Subject Disposition

Subject disposition will be summarized and listed for the ITT Set. Counts and percentages of subjects who completed the trial or discontinued from the trial, as well as the discontinuation reasons, will be summarized. Subject enrollment by site will also be summarized.

Subject counts and percentages in each category will be provided in the summary table. The number of enrolled subjects will be used as the denominator for calculating percentages.

7.2 Demographic and Baseline Characteristics

Patient characteristics such as patient age, gender, race, ethnicity, and height, weight, and BMI at baseline will be summarized for the ITT Set.

Continuous variables (including: age, height, weight, BMI) will be summarized using descriptive statistics. Categorical variables (including: gender, race, ethnicity) will be summarized using group frequencies and percentages, as appropriate.

7.3 Medical History

Medical history will be summarized and listed for the ITT Set. Medical history will be coded using system organ class (SOC) and preferred terms from the latest version of the Medical Dictionary for Regulatory Activities (MedDRA). The number and percentage of subjects within each SOC and PTs will be presented.

7.4 Inclusion/Exclusion Criteria

Inclusion and exclusion criteria failures will be provided in a listing for the ITT Set.

7.5 Protocol Deviations

Protocol deviations will be listed for the ITT Set. Protocol deviations may include but are not limited to deviation from informed consent, study procedure, study medication administration, or study restrictions. All protocol deviations will be reviewed by clinical and statistical teams to identify major protocol deviation prior to database lock.

Each protocol deviation will be classified into minor or major by subject matter experts based on ICH guidelines:

- Major: Major protocol deviations are defined as a subset of protocol deviations that may significantly impact the completeness, accuracy, and/or reliability of the study data or that may significantly affect a subject's rights, safety or well-being.
- Minor: Minor protocol deviations are defined as any change, divergence, or departure from the study design or procedures defined in the protocol. These deviations would not be expected to adversely affect the rights, safety or well-being of the subjects and/or the quality and integrity of data.

7.6 Treatment Administration and Study Duration

The extent of treatment will be summarized as follows:

- Descriptive statistics for Duration of study (months)
- The number and percentage of patients in the following categories of duration of study: <1 month, 1-<2 months, 2-<6 months, 6-<12 months, 12+ months. Study duration (days) is defined as last visit date dose date + 1, and 1 month = 30 days.

7.7 Concomitant Medications and Non-drug Treatments

Concomitant and non-drug treatments refer to all drug and non-drug treatments taken during the study, whether or not they are recorded at baseline (i.e., have stop day greater than or equal to day 1 relative to first dose of study drug). All medications will be classified using the latest version of World Health Organization Drug Dictionary (WHODD) coding dictionary. The Anatomical Therapeutic Chemical (ATC) classification and preferred term will be included after coded.

ATC and preferred term will be used to list and summarize the data. If a subject records multiple drugs with the same preferred term, these shall be summarized once within the count for N (%) of subjects.

8 STATISTICAL METHODS OF ANALYSIS

8.1 General Considerations

Efficacy and Safety analyses will be performed using the ITT Set. All data collected during the study for the ITT Set will be included in data listings.

8.1.1 Descriptive Statistics

For descriptive statistical summaries, continuous variables will be summarized by number of observations (n), mean, standard deviation (SD), standard error (SE), median, minimum (MIN), and maximum (MAX). For categorical variables, frequency/count and percentage of subjects in each category will be provided.

Minimum and maximum values will be presented at the same precision as the original value. Mean and median values will be rounded to one decimal place greater than the precision of the original value. SDs and SEs will be rounded to two decimal places greater than the precision of the original value. Percentages for summarizing categorical data will be rounded to one decimal place.

The by-subject listings, including data at scheduled and unscheduled visits, will be sorted by subject number, and then by date/time of the records.

8.1.2 Defining the Study Baseline

Baseline is defined as the last non-missing measurement obtained prior to the administration of the study drug for all efficacy and safety measures. Screening visits will not be summarized and will only be listed, unless an assessment taken at screening is considered baseline by definition.

8.1.3 Handling of Multiple Observations

For efficacy data, if multiple records were recorded for the same protocol-defined visit, the re-assayed data will be used for data summary and analysis. Re-assayed data from unscheduled visits will be treated similarly.

If a subject has a scheduled visit, the assessment obtained at the scheduled visit will be used for data summary and analysis. Otherwise, if no scheduled visit assessment exists but at least one unscheduled visit assessment is available within the protocol-defined visit window, then the data at the latest unscheduled visit within the protocol-defined visit window will be used for data summary and analysis.

Any unscheduled visits that cannot be attributed to a scheduled visit according to a protocoldefined visit window will not be included in descriptive statistical summaries but will be presented in listings.

8.1.4 Handling of Missing or Partial Data

- Missing baseline values will not be imputed in any situation.
- Missing post-baseline values for by-visit data will be summarized using the protocoldefined visit windows. If a value is not available within a given window, no imputation will be done.
- If day of birth is missing, the 1st day of the month will be used to calculate chronological age.
- Missing data for AE relationship will be imputed as "Related".
- For incomplete dates for AEs or non-study medications, the missing component(s) will be assumed as the most conservative value(s) possible. Actual data values, as they appear in the clinical database, will be shown in the data listings. Rules for partial dates are described in the table below. If the AE year is missing or AE is ongoing, the end date will not be imputed. Note: in the table, D = day, M = month, and Y = year.

| Parameter | Missing | Additional Conditions | Imputation |
|--------------------|------------|-----------------------------------|----------------------------------|
| Start date for AEs | Time only | | Time will not be imputed; but |
| | | | will be assumed to be after gene |
| | | | transfer time |
| | D only | M and Y same as M and Y of gene | Date of gene transfer |
| | | transfer date | |
| | | M and/or Y not same as M and Y | First day of non-missing month |
| | | of gene transfer date | |
| | D and M | Y same as Y of gene transfer date | Date of gene transfer |
| | | Y not same as Y of gene transfer | Use January 1 of non-missing |
| | | date | year |
| | M, D and Y | None – date completely missing | Date of gene transfer |
| Stop date for AEs | Time only | | Time will not be imputed |
| | D only | | Last day of non-missing month |
| | D and M | | Use December 31 of non- |
| | | | missing year |
| | M, D and Y | Deceased | Date of death |

| Parameter | Missing | Additional Conditions | Imputation |
|------------------|------------|-----------------------------------|--------------------------------|
| | | Not deceased | Date of the end of trial |
| | | | participation |
| Start date for | D only | M and Y same as M and Y of gene | Date of gene transfer |
| concomitant meds | | transfer date | |
| | | M and/or Y not same as M and Y | First day of non-missing month |
| | | of gene transfer date | |
| | D and M | Y same as Y of gene transfer date | Date of gene transfer |
| | | Y not same as Y of gene transfer | Use January 1 of non-missing |
| | | date | year |
| | M, D and Y | None – date completely missing | Date of gene transfer |
| Stop date for | D only | M and Y same as M and Y of gene | Last day of non-missing month |
| concomitant meds | | transfer date | |
| | | M and/or Y not same as M and Y | Last day of non-missing month |
| | | of gene transfer date | |
| | D and M | Y same as Y of gene transfer date | Use December 31 of non- |
| | | | missing year |
| | | Y not same as Y of gene transfer | Use December 31 of non- |
| | | date | missing year |
| | M, D and Y | None – date completely missing | Date will not be imputed |

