5.3. Screening and Enrollment

5.3.1. Screening Visits 1 and 2 (Day -45 through Day -1)

The screening evaluations will take place over two visits (preferentially two weeks apart) to allow time for ELISA and ELISPOT results to be available before the participant undergoes sedation/anesthesia and other invasive clinical assessments, as the former tests present a significant chance of being exclusionary and the latter assessments puts the children under additional risks and therefore should not be conducted unless the probabilities to be enrolled in the trial are high.

Each screening visit may take place over multiple consecutive days if deemed necessary by the Principal Investigator to accommodate all the clinical assessments that need to be performed.

The following evaluations will be conducted during Screening Visit 1:

- Informed consent process
- Demographics (including age, gender, race, and date of birth)
- Medical history (general and MPS related)
- A complete physical examination with a head circumference measurement
- Adverse events (upon ICF signature)
- Concomitant medications
- Vital signs (temperature, respiratory rate, heart rate, blood pressure)

- Height and weight
- The participant will be CCI walking a 25-meter distance
- CCI
- Echocardiogram
- ECG
- Lab work will include:
 - Complete blood cell count (CBC) and differential
 - Electrolytes
 - Serum/plasma total protein
 - Albumin
 - Prothrombin time (PT), partial thromboplastin time (PTT), international normalized ratio (INR)
 - Creatinine/Blood urea nitrogen (BUN)
 - Aspartate aminotransferase (AST), alanine transaminase (ALT), serum/plasma gamma-glutamyl transpeptidase (serum/plasma GGT)
 - Alkaline phosphatase
 - Amylase
 - Serum/plasma total bilirubin
 - Random glucose
 - Troponin
 - Plasma and leukocyte SGSH enzyme activity levels
 - Plasma heparan sulfate levels
 - CCI
 - Urine GAG and heparan sulfate levels
 - Urinalysis
 - Urine or Serum pregnancy test (if applicable)
- Samples for vector shedding (urine, saliva and feces)
- ELISpots for T-cell responses to AAV9 and SGSH
- ELISA for detection of total antibodies to AAV9 and antibodies to SGSH
- CCI
- Confirm diagnosis of MPS IIIA via gene sequencing (if not previously done)
- Cognitive function and adaptive functioning assessment using:

- Neurocognitive validity form (initial set up for first scales)
- Vineland Adaptive Behavior Scale II- Survey form, parental rating of adaptive functioning

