8.3 Safety Analyses

8.3.1 Adverse Events (AEs)

AE tables (except for AE overview table) will only include summaries of treatment-emergent adverse events (TEAE). TEAEs will be defined as those occurring during or after gene transfer on Visit 3 (Day 0). All AEs should be reviewed by Medical Monitor or Designee before the database is locked. All reported terms (investigator descriptions) for AEs should be reviewed by Medical Monitor or Designee before the database locked and will be coded using the latest version of MedDRA. Number and percentage of subjects with TEAEs will be summarized by system organ classification and preferred term.

An overview table will be provided with the number and percent of the following categories, if applicable:

- Number of total AEs, TEAEs, and deaths
- Incidence of patients with at least one: TEAE, TEAEs related to study treatment (IMP-related TEAE), SAE, IMP-related SAE, non-serious TEAEs, and deaths
- Incidence of patients who discontinued due to: TEAE, IMP-related TEAE, SAE, and IMP-related SAE
- Incidence of deaths and deaths due to IMP-related TEAE

TEAEs leading to discontinuation of study drug, IMP-related TEAE, serious TEAEs, nonserious TEAEs, and TEAEs by severity will be summarized and listed. Deaths will be listed, if any.

AEs occurring prior to gene transfer are defined as pre-treatment AEs and will be listed only.

AEs with relationship 'Possible', 'Probable', or 'Definitely' to IMP are defined as AEs related to study treatment.

Safety primary endpoint

• Product Safety as defined by the incidence, type and severity of treatment-related AEs and SAEs at Month 1, 2, 3, 6, 12

Product safety will be assessed by the incidences of treatment-related AEs and SAEs type and severity at each time point (<1 month, 1-<2 months, 2-< 3 months, 3-<6 months, 6-<12months, and >= 12 months from treatment date to AE onset date). Counts of subjects and percentages will be provided for baseline and post-baseline visits. Treatment-related AE is defined as AE that is 'Possible', 'Probable' or 'Definitely' related to study drug.

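### Three AE start-date rows in SAP 8.1.4 impute the gene-transfer date without checking the stop date, so an event recorded as over before infusion can be counted as treatment-emergent

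*SAP*

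**What the plan says.** SAP 8.1.4 opens its rule for incomplete AE and medication dates with a principle: "the missing component(s) will be assumed as the most conservative value(s) possible". A table then gives the rule row by row. For AE start dates, three rows return the gene-transfer date:

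- day missing, month and year as at dosing: "D only | M and Y same as M and Y of gene | Date of gene transfer"
- day and month missing, year as at dosing: "Y same as Y of gene transfer date | Date of gene transfer"
- nothing known: "None – date completely missing | Date of gene transfer"

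The remaining date rows return the start of the known period, for example "M and/or Y not same as M and Y | First day of non-missing month". A start on the dosing day without a time is assumed to fall after gene transfer. The same section imputes a missing relationship as related, for any AE.

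SAP 8.3.1 counts AEs occurring during or after gene transfer on Day 0 as treatment-emergent (TEAEs). For earlier ones it says "AEs occurring prior to gene transfer are defined as pre-treatment AEs and will be listed only". The primary safety endpoint tabulates treatment-related AEs and SAEs by time from treatment to onset, with a first bin of under 1 month. Protocol 5.3.1 starts AE collection at consent, within a screening period that runs from Day -45 to Day -1.

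**The concern.** The three rows depend only on which parts of the start date are missing and on whether the known parts match the dosing date. They ignore the one other field that can settle the question, the stop date. If the record shows that the event was over before infusion, there is no doubt left about treatment emergence for imputation to resolve. The table nevertheless places the start on Day 0. The result is an impossible record (start after stop) and an event that moves from a listing into the TEAE tables.

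Such events can plausibly occur. Screening Visit 2 includes a lumbar puncture and MRI under sedation or anesthesia, which may cause short-lived events that resolve before dosing. At stake are the TEAE tables of a five-subject gene-therapy study and, under a further condition on causality, its primary safety endpoint.

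**Working it through.** The plan states no figure on this point. The check applies the table literally to test cases and then bounds its reach.

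**Inputs.** Start-date table and relationship rule: SAP 8.1.4. TEAE definition and onset bins: SAP 8.3.1. Screening window of 45 days: Protocol 5.3.1. Number analysed, 5: SAP 5.1. The calendar dates below are assumed for illustration: gene transfer on 20 June 2021 and, in cases 1 to 3, a recorded AE stop on 10 June 2021.

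**Step 1: apply the table.**

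| Case | Start date as recorded | Imputed start | Start after stop? | Class under SAP 8.3.1 |
|---|---|---|---|---|
| 1 | June 2021, day missing | 20 June 2021 | Yes, by 10 days | TEAE |
| 2 | 2021, day and month missing | 20 June 2021 | Yes, by 10 days | TEAE |
| 3 | Completely missing | 20 June 2021 | Yes, by 10 days | TEAE |
| 4 | May 2021, day missing (stop 28 May 2021) | 1 May 2021 | No | Pre-treatment |
| 5 | 2020, day and month missing (stop 2 January 2021) | 1 January 2020 | No | Pre-treatment |

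The fault is confined to cases 1 to 3. An earlier known month, or an earlier known year, leaves the event pre-treatment.

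**Step 2: how much of the screening window each row can move.** Take all 365 dosing dates in a non-leap year and the 45 days before each: 365 × 45 = 16,425 possible onset days.

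- *Day missing.* Dosing on day d of a month leaves d − 1 earlier days in that month, from 0 to 30. The sum is 7 × 465 (31-day months) + 4 × 435 (30-day months) + 378 (February) = 5,373. Share: 5,373 / 16,425 = 32.7%.
- *Day and month missing.* The number of screening days in the dosing year is the smaller of 45 and the days already elapsed that year. The sum is 990 + 320 × 45 = 15,390. Share: 15,390 / 16,425 = 93.7%.
- *Completely missing.* 100%.

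These are shares of possible onset days, given that the date is partial in that way. They are not expected numbers of events.

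**Step 3: size per child.** Incidence counts subjects, so one child newly counted in a category adds 1/5 = 20 percentage points, and two add 2/5 = 40. A child who already has a genuine event in that category adds 0.

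**Step 4: route to the primary endpoint.** A moved event has onset at day 0, so it falls in the bin under 1 month. If it is non-serious, it is included only if its relationship is possible, probable or definite, or is missing and imputed as related.

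**The case against.** The strongest defence is that other text restrains the table. The lead-in asks for conservative values that are possible, and a start after a documented stop is not possible. SAP 8.3.1 classifies by when the event occurred. The Medical Monitor or designee reviews all AEs before lock, and the listings show the actual dates, so with 5 subjects an odd record should be noticed. These are safeguards and they reduce the risk. They are not a classification rule, and the explicit table is what will be programmed.

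The case against does limit the point, and it rules out several stronger readings that a reader might infer:

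- *All partial AE start dates move to Day 0.* They do not; see cases 4 and 5.
- *Resolved screening events go straight into the primary endpoint.* For a non-serious event, causality must also be recorded as related or be missing. Protocol 6.3 asks the investigator to assess causality for every event, so missing values should be few.
- *Each misdated event shifts incidence by 20 points.* That is a ceiling per category. Follow-up runs to Month 12, so a child may already have a genuine event there.
- *Concomitant medications are misclassified in the same way.* Their start-date rows can also give a start after the stop, but SAP 7.7 defines concomitant use by the stop day, so a drug stopped before dosing is excluded whatever start is imputed.
- *The stop-date rules distort results.* The text says "If the AE year is missing or AE is ongoing, the end date will not be imputed", while the table fills a completely missing stop date with the date of death or the end of participation. The contradiction is real, but TEAE status and the onset bins use the start date and SAP 8.3.1 plans no summary of AE duration.

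AEs are also collected at both screening visits, on Day -1 and on Day 0, and Protocol section 6 leaves out many Grade 1 events. An unknown onset with a known pre-dose resolution should therefore be uncommon.

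**Conclusion.** The point holds for the three rows that return the gene-transfer date. For an AE whose recorded stop precedes infusion, they produce a start after the stop and count as treatment-emergent an event that SAP 8.3.1 would otherwise only list. This needs no assumption about causality.

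The effect is at most 20 percentage points per misclassified child in any one category, and zero where that child already qualifies. The actual effect cannot be estimated, because the documents give no count of partial dates. The conclusion rests on reading the table as written, without an unwritten check against the stop date. The correction is worth making before database lock: the rule gives a wrong answer where the data already hold the right one, and with 5 subjects a single record can show in the tables.

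**What to change.** Add one condition to the three rows. Impute the gene-transfer date only if the recorded stop date, or its known components before any imputation, does not show that the AE ended before gene transfer. If it does show this, classify the AE as pre-treatment. Set its start to the later of the consent date and the first day of the known month or year (the consent date if the start is completely missing), and never later than the stop date.

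For cases 1 to 3, with consent assumed on 15 May 2021, this gives starts of 1 June, 15 May and 15 May, all before the 10 June stop. Cases 4 and 5 do not change. The test must use the stop date as recorded, because SAP 8.1.4 moves a stop with a missing day to the end of the month. If the stop is known only to be in the dosing month, timing is truly uncertain and the gene-transfer date can stay.

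Two lesser edits can go in at the same time: put the same bound on concomitant-medication starts, to avoid impossible dates, and reconcile the text and table on a completely missing AE stop date.

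The cost is a few sentences in the SAP and one condition in the derivation program. No new data are needed.
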